8.4.4 REPORTING OF PREGNANCY

While pregnancy itself is not considered an AE, pregnancy occurring in a clinical study must be followed to collect information regarding the experiences of gestation and pregnancy with study agent exposure. The investigator must report any pregnancy that occurs in a female study subject subsequent to first exposure to the study agent until End of Study, or 3 months following a subject's last dose. All pregnancies will be reported to the IRB, Sponsor, and CRO. In the event of a pregnancy, treatment will be discontinued, and the subject will undergo continued safety follow-up through pregnancy outcome.

Any pregnancy must be followed by the investigator until delivery or to the end of pregnancy. Any anomalies, complications, abnormal outcomes, or birth defect observed in the child must be reported as an SAE within 24 hours of the investigator or study personnel's first knowledge.

8.5 STUDY HALTING RULES

If any of the following safety events occur, a Safety Evaluation Meeting (defined below) will be triggered:

- Three or more SAEs in the same system/organ/class (SOC) that are assessed as possibly or definitely related to the study agent by the investigator and confirmed as such by the Sponsor (see [Section 8.2.2 Relationship to Study Agent](#)).
- Within or between any of the dosing groups: an overall pattern of symptomatic, clinical, or laboratory events associated with the study agent that the Sponsor's Program Physician or designee consider a serious potential safety concern (e.g. suspicious overall pattern).

Events that are more likely related to the infusion procedure, such as infiltration or hematoma, will not be considered "drug related" and will not contribute to the count of definitely-related SAEs that would trigger a Safety Evaluation

Meeting.

Safety Evaluation Meeting

If safety events of potential concern occur during the trial (as defined above) a Safety Evaluation Meeting will be triggered, and dosing may be temporarily halted based on the observations. The Sponsor will inform investigators and the FDA in the event of any temporary halt in dosing at any time during the conduct of the study. The purpose of the meeting is for investigators, the Sponsor, and the CRO Medical Monitor to discuss and evaluate the safety of the subjects using available aggregated safety data and without compromising study blinding.

Attendants at the Safety Evaluation Meeting will include the Alkahest Program Physician (or his/her designee), the CRO Medical Monitor, and a majority of active investigators participating in the trial. After sufficient data review the Sponsor will choose one of the following courses of action:

1. Continue dosing with no change to protocol.
2. Halt dosing in all groups and stop the study.
3. Continue with a modified protocol design and amend the protocol as appropriate.

8.6 SAFETY OVERSIGHT

Safety oversight will be provided by the Sponsor's Program Physician or his or her designee and the CRO's Medical Monitor in concert with the Principal Investigators at each participating site. As all subjects are on active drug, there will be no formal Data Safety Monitoring Board (DSMB) established. As needed, blinded Safety Evaluation Meetings will be convened as described in [Section 8.5](#) to monitor the ongoing safety of the study. The Sponsor's Program Physician or designee is the final authority for safety oversight in the study.

9 CLINICAL MONITORING

Clinical site monitoring is conducted to ensure that the rights and well-being of human subjects are protected, that the reported trial data are accurate, complete, and verifiable, and that the conduct of the trial is in compliance with the currently approved protocol/amendment(s), with GCP, and with applicable regulatory requirement(s).

- Monitoring for this study will be performed by the Study CRO in accordance with the Clinical Monitoring Plan (CMP).
- A mix of on-site and centralized risk-based monitoring will be performed to ensure the safety of clinical subjects and the accuracy and completeness of study data.
- The Sponsor will be provided with copies of monitoring reports per the timelines specified within the CMP.
- Details of clinical site monitoring are documented in the Study's CMP. The CMP describes in detail who will conduct monitoring, at what frequency monitoring will be done, at what level of detail monitoring will be performed, and the distribution of monitoring reports.
- Independent audits may be conducted by the Sponsor in accordance with the Sponsor's clinical quality oversight plan or equivalent to ensure monitoring practices are performed consistently across all participating sites and that monitors are following the CMP.

10 STATISTICAL CONSIDERATIONS

10.1 STATISTICAL AND ANALYTICAL PLANS

A Statistical Analysis Plan (SAP) with analytical details and assumptions will be developed during the conduct of the study. The finalization of the SAP will occur prior to clinical database lock and unblinding of the study data.

10.2 STATISTICAL HYPOTHESES

In as much as the study design is focused on safety and tolerability, the statistical approach toward the secondary endpoints will be primarily descriptive with only modest amounts of hypothesis testing; within-subject changes from baseline for each dosing group and among-group differences will be evaluated.

10.3 ANALYSIS DATASETS

Four analysis datasets are possible however, analyses may not necessarily be conducted with all four:

- **Intention-to-Treat (ITT) Dataset:** all randomized participants.
- **Safety Dataset:** all subjects who received at least one dose of the study agent.
- **Evaluable Dataset:** all subjects who receive at least 5 of the 10 planned doses.
 - **Per Protocol Dataset:** a subset of the Evaluable Dataset comprised of subjects who have no Major Protocol Deviations.

The presentation of baseline characteristics will be conducted on the ITT dataset. All safety analyses will be performed for the Safety Dataset. Analyses of the secondary endpoints will focus on the Evaluable and/or Per Protocol Datasets.

10.4 DESCRIPTION OF STATISTICAL METHODS

10.4.1 GENERAL APPROACH

Using the Evaluable and/or Per Protocol Datasets, all secondary cognitive-score endpoints (e.g., MMSE, ADAS-Cog, etc.) will be summarized serially over time using descriptive statistics to assess the within-subject changes and among-group differences. Overall baseline and demographic data will be summarized using descriptive statistics; among-groups testing will be used to evaluate the effectiveness of the randomization in producing homogeneous pre-treatment groups.

For analysis of the primary and secondary endpoints, the following will be considered:

- For endpoints that are continuous in nature:
 - Number of observations, mean, median, minimum and maximum, and standard deviation (SD) values will be presented as descriptive summary.
 - For inferential statistics:
 - If the Normality assumption is met, Paired t-test, or Analysis of Covariance (ANCOVA) using the baseline value as a covariate will be used.

- If the Normality assumption is not met, a rank –ANCOVA analysis i.e., an ANCOVA analysis on rank-transformed data or other non-parametric methods will be used.
- For endpoints that are categorical in nature:
 - Frequency counts and percentages will be presented as descriptive summary.
 - Chi-square test or Logit model will be used for inferential statistics.

Subject disposition (e.g., the number of subjects randomized, completed, and discontinued) will be summarized and medical history data will be listed. Prior and concomitant medications taken from screening and during the study will be categorized by World Health Organization (WHO) classification for therapeutic class and drug name, listed and summarized by number and percentage of subjects.

Final analyses are not limited to the summaries described herein. As noted above, analytical details and assumptions will be fully presented in the SAP.

10.4.2 ANALYSIS OF THE PRIMARY ENDPOINT(S)

Summary tabulations of the reported adverse events will be presented by group after the Verbatim Terms have been coded to PTs and SOCs using the MedDRA Version 21.0 coding dictionary. The summaries will include severity and attribution to the study agent. Multiple reports of the same AE by the same subject will be counted only once at the highest severity and strongest attribution to the study agent.

The AE analyses will focus on those that are Treatment-Emergent, however any AEs that are reported after consent has been signed and prior to initial dosing will be tabulated as Intercurrent Events.

Additional details are presented in [Section 10.4.4](#).

10.4.3 ANALYSIS OF THE SECONDARY ENPOINT(S)

The study is not designed to detect significant changes in cognition over time. However, using available data from analysis of the secondary endpoints, including changes in cognition scores from baseline, descriptive summarization will be developed. Of particular interest will be the within-subject changes from baseline and their distribution around a null value of zero and a comparison among groups to evaluate any trends in dose response. Appropriate paired sample tests (paired t-test or Wilcoxon Signed Rank tests) may be conducted to evaluate within-subject changes from baseline, using a two-tailed α -level of 0.05. Among-group differences may be assessed by One-way ANCOVA or its nonparametric equivalent test. Alternatively, since the dose groups are ordinal, regression and graphical methods may be employed to evaluate any dose-response trends.

10.4.4 SAFETY ANALYSES

Safety, tolerability, and feasibility will be evaluated by examining the occurrence of AEs, including Treatment-Emergent AEs, and AEs leading to discontinuation from the study. AEs will be summarized by severity and by study drug dose.

Actual and changes from baseline in clinical laboratory measurements and vital signs will also be assessed and summarized. Abnormal values will be determined and flagged in the listings. Laboratory shift tables or graphics displaying the change (number of subjects) relative to the reference range from baseline to each study visit may also be presented for each test. The investigator should exercise his or her medical and scientific judgment in

deciding and documenting whether an abnormal laboratory finding, or other abnormal assessment is clinically significant.

Per-subject extent of exposure will be listed.

10.4.5 ADHERENCE AND RETENTION ANALYSES

Feasibility as measured by subject adherence with the study visit schedule, visit procedures, infusions, and subject retention. Subject adherence may vary across the different groups offering another feasibility measurement as would a comparison of the number of subjects who complete two series of 5 pulsed doses to subjects who complete only the first series. Reasons for study discontinuation will be compared across groups and across other subgroups of subjects, as appropriate.

10.4.6 BASELINE DESCRIPTIVE STATISTICS

See [Section 10.4.1](#).

10.4.7 PLANNED INTERIM ANALYSES

No interim analyses are planned. If a Safety Evaluation Meeting is triggered (see [Section 8.5](#)), an ad hoc interim safety analysis will be performed. If such an ad hoc safety interim analysis is conducted, the dose assignment will remain masked.

10.4.8 ADDITIONAL SUB-GROUP ANALYSES

Not applicable.

10.4.9 MULTIPLE COMPARISON/MULTIPLICITY

No adjustments for multiplicity will be employed.

10.4.10 TABULATION OF INDIVIDUAL RESPONSE DATA

This will be further defined in the SAP.

10.4.11 EXPLORATORY ANALYSES

Not applicable.

10.5 SAMPLE SIZE

A total of 40 subjects (20 in the 100 mL group and 20 in the 250 mL group) will be randomized in the study with the intent of obtaining ~30 evaluable subjects who have received at least 5 doses and completed through Visit 8. Subjects who discontinue prior to completing Visit 8 may be replaced. Subjects who withdraw or are withdrawn during screening will be replaced. Subjects who are randomized but do not receive any dose of the study agent, may be re-screened and randomized if they meet all of the study eligibility requirements.

The study is not powered for detecting statistically significant differences in pharmacodynamic parameters or to assess the cognitive effects of GRF6019 infusions in AD. However, using the statistical approximation described by Hanley (aka the “Rule of Threes”), the upper bound of the 95% confidence interval for the rate of an unreported AE is at most 5.0% (3/number of subjects receiving active drug). In addition, the proposed sample size may be sufficient to identify trends in the effects of plasma-derived factors and in the relationship between dose and response.

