- Changes in the Clinical Dementia Rating Scale – Sum of Boxes (CDR-SOB).
- Changes in the Alzheimer’s Disease Cooperative Study – Activities of Daily Living₂₃ (ADCS-ADL₂₃).
- Changes on the Alzheimer’s Disease Cooperative Study – Clinical Global Impression of Change rating (ADCS-CGIC).
- Changes on the Neuropsychiatric Inventory Questionnaire (NPI-Q).
- Changes in the Savonix Neurocognitive Assessments and Digit Span.

Secondary safety endpoints will be assessed as follows:

- Changes from baseline in clinical laboratory parameters.
- Changes from baseline in vital sign measurements.
- Changes from baseline in the Columbia-Suicide Severity Rating Scale (C-SSRS).
- Changes on MRI scans designed to assess for Amyloid Related Imaging Abnormalities (ARIA).

Secondary feasibility endpoint will be assessed by:

- Subject compliance with the study visit schedule and study visit procedures
- Subject retention
- Success of blinding

Exploratory endpoints will be assessed as follows:

- Changes in imaging endpoints such as volumetric MRI (vMRI), functional MRI (fMRI), and Arterial Spin Labeling (ASL)
- Changes in blood-based biomarkers
- Changes in CSF biomarkers (in participating subjects)

Population: Approximately 40 subjects between 60 and 90 years of age with a diagnosis of probable mild to moderate AD. Assuming a drop-out rate of 25%, enrollment at this level will yield approximately 30 evaluable subjects.

Phase: 2

[figure not shown]
Number of Sites: Up to 10 sites in the United States

Description of Study Agent: GRF6019: A ██████ human plasma protein fraction for IV infusion

Study Duration: Approximately 15 months

Participant Duration: Approximately 7 months

SCHEMATIC OF STUDY DESIGN

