4.2 STUDY ENDPOINTS

4.2.1 PRIMARY ENDPOINTS

The primary endpoints in this study pertain to the safety, tolerability and feasibility of each dose level.

Safety endpoints are as follows:

- Incidence of treatment-emergent adverse events (AEs) identified by MedDRA preferred term (PT) and grouped by MedDRA System Organ Class (SOC).

Tolerability endpoints are as follows:

- Number of subjects completing 8 weeks (i.e. through Visit 10) after receiving at least 5 infusions.
- Number of subjects completing 24 weeks (i.e. through End of Study) after receiving at least 10 infusions.

Feasibility endpoints are as follows:

- Number of subjects completing 5 and 10 infusions.

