18 REVISION HISTORY

**Protocol Version 7.0 dated 02NOV2018
Replaces: Protocol Version 6.0 dated 12OCT2018**

In this table, changes from Version 6.0 dated 12OCT2018 are described and their rationale is given.

Location	Description	Purpose
Throughout	Protocol Version previously read: v6.0_12OCTMAR2018 Now reads: v7.0_02NOV2018	Version control.
[REDACTED]	[REDACTED]	[REDACTED]
Throughout	Grammar and style changes	For protocol clarity and standardization.
List of Definitions, Protocol Summary	The Infusion Period will be now be between 2 hours to a maximum of 3 hours.	The Infusion Period was previously increased to from 2.0 to 2.5 hours to 2.5 to 3 hours; to maintain blinding and continuity, all patients will now be infused between 2 hours to a maximum of 3 hours.
Protocol Summary, 4.1 Description of the Study Design	Extension of study duration to ~19 months was reverted to ~15 months and recruitment period of ~12 months was reverted to ~8 months.	Study duration and recruitment period were decreased as additional subjects will not be needed [REDACTED]
2.2 Rationale	Text content and Table 1 changed to reflect revised dosing.	Required changes [REDACTED]
7.3.3 Randomization, 10.5 Sample Size	The following sentence was added to both sections, "Subjects who are randomized but do not receive any dose of the study agent, may be re-screened and randomized if they meet all of the study eligibility requirements."	Content added to clarify potential re-screening for eligible subjects.
17 Schedule of Events	Note "c": removed propoxyphene from urine drug screen.	Screening for this substance is not required.

Protocol Version 6.0 dated 12OCT2018
Replaces: Protocol Version 5.0 dated 30AUG2018

In this table, changes from Version 5.0 dated 30AUG2018 are described and their rationale is given.

Location	Description	Purpose

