7.3 Study Schedule / 17 Schedule of Events	
 Amended the Study Schedule and Schedule of Events to include i-STAT labs on V4, V6, V8, V12, V14, and V16. Amended the Study Schedule and Schedule of Events to include the following per Clarification Memo #4: “Note: subjects randomized prior to August 30, 2018, will not participate in the additional interim safety labs at Visit 9 and Visit 17.” 	
 Added i-STAT lab evaluations for increased safety monitoring after FDA request. Per Protocol V5.0 (30AUG2018), blood samples are to be collected at Visit 9 and Visit 17 for interim safety labs. However, subjects who were randomized prior to August 30, 2018, will not participate in the additional interim safety labs at Visit 9 and Visit 17 since they will be following the previous protocol version.

Protocol Version 5.0 dated 30AUG2018
Replaces: Protocol Version 4.0 dated 27MAR2018

In this table, changes from Version 4.0 dated 27MAR2018 are described and their rationale is given.

Location	Description	Purpose
Title Page, Protocol Approval Page, 1.1 Authorized Representative (Signatory) / Responsible Party	Updated Sponsor’s mailing address and authorized representative.	Administrative.
Throughout	
Protocol Version Previously read: v4.0_27MAR2018
 
Now reads: v5.0 30AUG2018
	Version control.
[REDACTED]	[REDACTED]	[REDACTED]

Location	Description	Purpose
List of Definitions / Protocol Summary	Extended the Infusion Period to be a maximum of 3 hours.	Infusion rates will be adjusted such that the Infusion Period will be of approximately the same duration for all doses (e.g., 100 mL, 250 mL, [REDACTED]).
Protocol Summary, 4.2.2 Secondary Endpoints, 7.1.1.2 Procedures to Assess Safety	Moved the following from list of exploratory endpoints to secondary safety endpoints: “Changes on MRI scans designed to assess for Amyloid Related Imaging Abnormalities (ARIA)” and updated other sections of the Protocol accordingly.	Evaluating changes on MRI scans to assess for ARIA is a secondary safety endpoint.
Protocol Summary, 4.1 Description of the Study Design	Extended study duration to ~19 months.	To account for extended recruitment period to enroll an additional 20 subjects.
2.2 Rationale	Incorporated isometric scaling as rationale for human dosage levels.	Isometric scaling may be the most likely to accurately estimate the human potential effective dose.

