1.3 Sample Size Estimation

A total of approximately 40 subjects (20 in the 100 mL and 20 in the 250 mL groups) will be randomized in the study with the intent of obtaining ~30 evaluable subjects who have received at least 5 doses and completed through Visit 8. Subjects who discontinue prior to Visit 8 may be replaced. Subjects who withdraw or are withdrawn during screening will be replaced.

The primary endpoint of this study is safety and tolerability. Using the statistical approximation described by Hanley (aka the “Rule of Threes”), the upper bound of the 95% confidence interval for the rate of an unreported AE is at most 7.5% (3/number of subjects receiving active drug). In addition, the proposed sample size may be sufficient to identify trends in the effects of plasma-derived factors and in the relationship between dose and cognitive effects.

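### Protocol 10.5 gives a 5.0% upper bound for the rate of an unreported adverse event; its own formula with its planned 40 subjects gives 7.5%, the figure in SAP 1.3

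*Protocol*

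**What the plan says.** Protocol section 10.5 sets the size of the trial: "A total of 40 subjects (20 in the 100 mL group and 20 in the 250 mL group) will be randomized". It says the study is not powered for cognitive or pharmacodynamic effects. It then describes what the sample offers for safety, using the Rule of Threes for the upper 95% confidence bound on an event that is never observed: "the rate of an unreported AE is at most 5.0% (3/number of subjects receiving active drug").

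Every subject counts in that denominator. Both arms (100 mL and 250 mL) are active, and section 8.6 gives this as the reason for having no data safety monitoring board: "As all subjects are on active drug".

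SAP section 1.3 repeats the statement for approximately 40 subjects, 20 per dose, with the same formula and a different result: "the rate of an unreported AE is at most 7.5% (3/number of subjects receiving active drug"). SAP section 8, which lists changes from the protocol, does not mention the difference.

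**The concern.** The formula, the denominator and the result stand together in Protocol 10.5, and the result does not follow from the other two. The SAP, which says it is to be read together with the protocol, gives a different number from the same inputs. Both cannot be right.

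Safety is the primary objective, efficacy is expressly unpowered, and this bound is the only numerical statement of what the sample can rule out. An investigator or ethics committee reading the protocol would conclude that an event not seen in the trial has a rate of at most 5.0%. If the correct bound is higher, the protocol claims to exclude rates that the trial cannot exclude.

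**Working it through.** **Inputs**

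- Formula: 3/n, with n the number of subjects receiving active drug (Protocol 10.5, SAP 1.3).
- Planned n: 40, as 20 + 20 (Protocol 10.5); approximately 40 (SAP 1.3).
- Share on active drug: all (Protocol Summary; Protocol 8.6).
- Assumed drop-out: 25%, leaving about 30 evaluable (Protocol Summary).

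**Trying to reproduce the protocol's 5.0%**

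- Planned number: 3/40 = 7.5%. The protocol figure is not reproduced; the SAP figure is.
- Solving for n: 3/0.05 = 60 subjects.

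**Other denominators**

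| n | Source | 3/n |
|---|---|---|
| 20 | one dose group | 15.0% |
| 30 | evaluable subjects | 10.0% |
| 40 | all planned subjects | 7.5% |
| 60 | not planned in the visible current text | 5.0% |

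**Other ways of calculating a bound with zero events at n = 40**

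- Exact one-sided 95%: 1 − 0.05^(1/40) = 7.2%.
- Exact two-sided 95% (Clopper-Pearson): 1 − 0.025^(1/40) = 8.8%.
- Wilson: 6.3% one-sided, 8.8% two-sided.
- Jeffreys: 4.7% one-sided, 6.0% two-sided.

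None of these equals 5.0%. The one-sided Jeffreys value is the only one below it, and it is not the method the protocol names.

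**Could replacement of subjects raise n to 60?** Protocol 10.5 allows replacement of subjects who discontinue before completing Visit 8. The documents do not say how many of the assumed 25% would leave that early, so these two cases are illustrations that assume all of them do:

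- Each drop-out among the first 40 is replaced once: 40 + 0.25 × 40 = 50 dosed, and 3/50 = 6.0%.
- Replacement continues until 40 are retained: 40/0.75 = 53.3, rounded up to 54 dosed, and 3/54 = 5.6%.

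Both stay above 5.0%. Reaching 60 would take 20 extra dosed subjects, half the planned enrolment.

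**What the error means.** For an event with a true rate of 5.0%, the chance of seeing none is:

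- in 40 subjects: 0.95^40 = 12.9%;
- in 60 subjects: 0.95^60 = 4.6%.

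A 95% bound should leave about 5%. At 40 subjects, 5.0% does not meet that standard.

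**A possible origin.** The revision history (section 18) records for version 5.0: "To account for extended recruitment period to enroll an additional 20 subjects". For version 7.0 it records: "Study duration and recruitment period were decreased as additional subjects will not be needed". Since 40 + 20 = 60, the 5.0% may have been left behind when the plan returned to 40. This is inference from a log of superseded text, and the finding does not rest on it.

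**The case against.** The best counter-argument concerns weight. The bound did not determine the sample size. The safety meeting trigger in Protocol 8.5 is a count of related serious events or a judged pattern. Adverse events are tabulated, with no formal testing planned. Protocol 10.1 leaves analytical detail to the SAP, and the SAP already has the right figure. All of this is correct. It limits the consequence, but it leaves the protocol with a wrong number that the SAP contradicts.

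Several narrower objections also have force:

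- SAP section 8 deals with changes to planned analyses. A sample-size remark need not appear there, so its absence is not a separate fault.
- The figures of 50 and 54 dosed subjects are assumptions. The 25% drop-out is already built into going from 40 enrolled to about 30 evaluable, and Protocol 5.3 ties replacement to having enough evaluable subjects, not to restoring 40. Protocol 10.6.3 also provides for replacing subjects unblinded before dosing day 5, which the two cases leave out.
- The protocol does not say whether its bound is one-sided or two-sided. One-sided is the usual reading of 3/n, and the exact two-sided limit at 40 is higher still (8.8%).
- Parts of the revision history and of the SAP's treatment-group text are blacked out, so only the visible text can be said to lack a plan for 60.

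None of these points makes 3/40 equal to 5.0%. The planned number in Protocol 10.5 is legible and the sentence is intact, so neither redaction nor text extraction explains the figure.

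**Conclusion.** The concern holds. With the 40 subjects planned, all on active drug, the formula printed in Protocol 10.5 gives 7.5%. The printed 5.0% is too low by a factor of 7.5/5.0 = 1.5. If no event is seen in 40 subjects, rates between 5.0% and about 7.5% remain compatible with the data, although the protocol says they are excluded.

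The conclusion assumes only that the denominator is the planned number dosed. Fewer dosed subjects would widen the bound, and the illustrative replacement cases do not bring it down to 5.0%. It is a definite error in the only stated precision figure for the primary objective. Its practical reach is small, because no test, halting rule or enrolment decision uses it.

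**What to change.** In Protocol 10.5, replace 5.0% with 7.5%, so that it agrees with SAP 1.3. It would help to label the figure as pooled over both doses at the planned 40 subjects and as a one-sided 95% bound (exact value 7.2%).

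The cost is one number in a protocol text amendment, which section 12.2 requires to go to the IRB/IEC. The stated precision becomes less favourable. Enrolment, analyses and procedures do not change.

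One addition is optional and corrects no printed figure. Protocol 4.2.1 sets the primary endpoints by dose: "The primary endpoints in this study pertain to the safety, tolerability and feasibility of each dose level". One sentence in Protocol 10.5 and one in SAP 1.3 could therefore give the bound per dose group at 20 subjects: 3/20 = 15% (exact one-sided: 1 − 0.05^(1/20) = 13.9%).
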